### **Randomization:**

[figure not shown]
After obtaining an informed consent, study staff will complete a baseline assessment consisting of measures of cognition, physical function, depression and anxiety, and quality of life (see measures section 4.3.l. below). Blood samples will also be collected from the participants at the time of baseline assessment. Baseline may be completed at subject's home after hospital discharge if unable to complete full assessment in the hospital. After initial assessment, study subjects will be randomized to study groups. Randomization will be stratified by discharge location (home, other facility) and managed by the IU site

[During COVID-19 health crisis, baseline assessments will be completed via phone; abbreviated measures of cognition, and no measures of physical function will be obtained due to the limitations of phone administration. Blood samples will not be collected.]

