## 8. Statistical Considerations

To verify the comparability of the randomized groups, patients' baseline characteristics among the four groups will be compared using analysis of covariance (ANCOVA) for continuous variables and the Cochran-Mantel-Hansel statistic for categorical variables while adjusting for age group. We will examine the distributions of continuous variables and use alternative approaches such as transformation or nonparametric methods in cases of violation to the normal distribution assumption. We will also examine the frequency distribution of all categorical variables and adopt exact inference procedures in cases of zero or small cell size. All analyses will be conducted using the SAS 9.4 (SAS Institute, Carey, North Carolina).

**Primary Specific Aim:** Mixed effects models will be used with repeated RBANS scores collected at baseline, 3 months and 6 months as the outcome measures, group, time and a group by time interaction as independent variables while adjusting for stratification variables and other potential baseline covariates found to be significantly different in univariate comparisons. A significant interaction between group and time would indicate differences in changes of cognitive functions over time among the four groups. Post-hoc comparisons will be conducted following a significant interaction between group and time to compare the effect of the combined training group to the other three groups (attention control, cognitive training only, and exercise only groups) at 3 month for immediate training effect and at 6 month for sustained training effect. Separate mixed effect models will also be used for repeated, Trail Making A&B, and Stroop Color and Word Test scores.

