**Secondary Specific Aim 1:** Separate mixed effects models will be used with repeated measures (SPPB, 2-minutes step, PHQ-9, GAD-7, SF-36 PCS and MCS) as the outcome variables, group, time and interactions between group and time as independent variables while adjusting for stratification variables and other baseline covariates that may be different among the four groups. Significant interactions between group and time in these models would indicate differences in changes of functional outcomes, depressive symptoms, and anxiety levels or quality of life over time among the four groups. Post-hoc analyses will also be conducted following significant interactions in the mixed effects models to compare the combined training group to the other three groups and to determine how early a group difference can be detected and whether the effect extends beyond the training period.

**Exploratory Aim 1:** Changes in the serum levels of CRP, IL-1, IL-6, IL-8, TNF-  $\alpha$ , S-100 $\beta$ , GFAP, BDNF, VEGF, and IGF-1 will be calculated and used as the dependent variables in ANCOVA models with group as the independent variable and adjusting for stratification variables and baseline covariates that are

found to be different among the groups in univariate comparisons. Post-hoc comparisons will be used following a significant group effect to compare biomarker levels in the combined training group to the other three groups.

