Sample Size and Power: Cognitive training had been found to have a moderate effect size of approximately 0.5 SD and the combined training was found to have a larger effect size of 0.9 SD when comparing to the control group in healthy elderly subjects. Assuming effect sizes of 0.4 SD in the cognitive training only group and the exercise only groups at 3 and 6 month post baseline compared to the attention control group and effect size of 0.8 SD in the combined training group at 3 and 6 month post baseline compared to the attention group, a sample size of 60 patients in each group will yield 83% power at detecting a significant group by time interaction in a mixed effect model adjusting for correlations of 0.2 for outcomes measured 3 month apart and correlations of 0.1 for outcomes measured 6 month apart at  $\alpha=0.05$ . The power estimation was conducted using the GLMPower procedure in SAS. To further assume that 30% patients may miss some post-baseline assessments, we will need to enroll a total of 344 patients into the study (86 patients per group). Outcomes in Secondary Aim 1 will also have 83% power to detect effect sizes similar to those described for the Primary Aim. For Secondary Aim 2, we will have 81.7% power to detect an overall treatment effect in changes in biomarkers with effect sizes of 0.31 SD in the cognitive training only and the exercise only groups and 0.62 SD in the combined training groups at  $\alpha=0.05$  using one-way ANOVA and the Power procedure in SAS.

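### As listed, without covariate-by-time terms, the stratification and covariate adjustment leaves the primary group-by-time test unchanged with complete data and almost unchanged under the planned 30% missingness

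*Combined protocol and SAP*

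**What the plan says.** The Primary Specific Aim paragraph of Section 8 makes the baseline score part of the response: "Mixed effects models will be used with repeated RBANS scores collected at baseline, 3 months and 6 months as the outcome measures". The terms are "group, time and a group by time interaction as independent variables while adjusting for stratification variables and other potential baseline covariates", the covariates being those that differ significantly between groups at baseline. The test is interpreted as change: "A significant interaction between group and time would indicate differences in changes of cognitive functions over time among the four groups". If it is significant, the combined group is compared with each other group "at 3 month for immediate training effect and at 6 month for sustained training effect".

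Secondary Specific Aim 1 repeats the structure for six outcomes (SPPB, 2-minute step, PHQ-9, GAD-7, SF-36 PCS and MCS): "group, time and interactions between group and time as independent variables while adjusting for stratification variables and other baseline covariates".

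On the stratification factor, Section 4 says "Randomization will be stratified by discharge location (home, other facility"). The baseline comparisons that open Section 8 use ANCOVA and "the Cochran-Mantel-Hansel statistic for categorical variables while adjusting for age group".

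Section 8 neither lists nor excludes a covariate-by-time term. It does not name the covariance structure or say whether time is categorical.

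**The concern.** The adjustment is the plan's stated response to baseline imbalance, and the usual reason to carry a stratification factor into the model is precision. Both purposes concern the quantity tested, which is change. A main effect acts on a patient's level, not on change, so it serves neither purpose in the interaction test.

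Two things are at stake. First, a report could call the primary test adjusted for a variable that predicts recovery while its imbalance remains in the result. Second, if recovery differs by discharge location, that variation stays in the error term although randomisation was stratified on it. The same applies to the six Secondary Aim 1 models. By contrast, Exploratory Aim 1 uses change in the biomarker as the dependent variable of an ANCOVA, and there a covariate main effect does adjust change.

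**Working it through.** **1. The plan's own figure.** Inputs from the Sample Size paragraph: 60 per group; 0.4, 0.4 and 0.8 SD over control at both follow-ups; correlations 0.2 (3 months apart) and 0.1 (6 months apart); alpha 0.05.

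- Variance of the 3-month change: 2(1 − 0.2) = 1.6. Of the 6-month change: 2(1 − 0.1) = 1.8. Covariance: 1 − 0.2 − 0.1 + 0.2 = 0.9.
- Group deviations from the mean of 0.4 are −0.4, 0, 0, 0.4, so the sum of squares is 0.32, and 60 × 0.32 = 19.2.
- Noncentrality: 19.2 × (1.6 + 1.8 − 2 × 0.9)/(1.6 × 1.8 − 0.9²) = 19.2 × 1.6/2.07 = 14.84.
- Power is 83.3% (Hotelling-Lawley) or 82.6% (Wilks). The plan's 83% is reproduced without any covariate. Also 60/0.7 = 85.7, so 86 per group and 344 in total.

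**2. Algebra with complete data.** Write the score of patient i in group g at visit t as Y(i,t) = μ(g,t) + γx(i) + e(i,t), where x does not change over time. Then Y(i,t) − Y(i,0) = μ(g,t) − μ(g,0) + e(i,t) − e(i,0). The term γx(i) is gone. With γ(t) in place of γ, which is a covariate-by-time term, (γ(t) − γ(0))x(i) remains and is adjusted.

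**3. Effect on the test.** REML fits to simulated trials, plan correlations, assumed covariate effect 0.27 SD, random-intercept and unstructured covariance, comparing main effects with no covariates:

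| Data | Largest shift in an interaction estimate | Shift in F |
|---|---|---|
| Complete, 60 per group | about 1e-14 | at most 4e-6 (optimiser noise) |
| 30% missing follow-up, 86 per group | 0.05 to 0.07 SD | mean 0.08 to 0.12, largest 0.32 |

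With missing data, standard errors moved by up to 1.7%, and 1 of 120 trials changed its verdict at 0.05. With assumed correlations of 0.7/0.6 and a random intercept, F moved by 0.23 to 0.25 on average and at most 0.78.

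**4. Imbalance that predicts change.** Assumed, not in the documents: a 0.4 SD imbalance between combined and control, and 0.3 SD of change per SD of the covariate. Expected false change: 0.4 × 0.3 = 0.12 SD. Three sets of simulated trials with no treatment effect, 3-month change, combined minus control:

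| Setting | No covariate | Main effect | Covariate-by-time | Removed by covariate-by-time |
|---|---|---|---|---|
| Complete, 60 per arm | 0.132 | 0.132 | 0.004 | 0.128 |
| Complete, 60 per arm | 0.145 | 0.145 | 0.024 | 0.121 |
| Complete, 60 per arm | 0.158 | 0.158 | 0.041 | 0.117 |
| 30% missing, 86 per arm | 0.143 | 0.144 | 0.027 | 0.116 |
| 30% missing, 86 per arm | 0.143 | 0.142 | 0.026 | 0.117 |
| 30% missing, 86 per arm | 0.099 | 0.098 | −0.016 | 0.115 |

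Monte Carlo error on a single mean is about 0.03 SD at 60 trials, so the levels are rough. The columns compare the same simulated trials: the main effect removes essentially nothing, and covariate-by-time removes about 0.12.

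**5. Contrasts read as visit means.** Under the same assumptions the covariate's effect is 0, 0.3 and 0.3 at the three visits. A single coefficient averages these to about 0.2. The false difference at 3 months becomes about 0.12 − 0.4 × 0.2 = 0.04, and at baseline 0 − 0.08 = −0.08. The visit mean is partly corrected, while the change is still 0.04 + 0.08 = 0.12. In 1,000 simulated trials the 3-month difference fell from 0.124 to 0.045.

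**6. Precision.** Assume 40% are discharged to a facility and their 3-month change differs by d. Share of variance = 0.24d²/(1.6 + 0.24d²), with 0.24 = 0.4 × 0.6. For d = 0.5: 0.06/1.66 = 3.6%. For d = 0.8: 0.1536/1.7536 = 8.8%. Applying that share R² to both follow-ups, noncentrality is 14.84/(1 − R²), and 83% becomes about 85% to 87%.

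**The case against.** The strongest reply is that the wording is not a full model statement. Adjusting for a variable does not exclude its interaction with time, and a statistician might include it. That stands: the absence is inferred from a list that names only one interaction. It is also a reason to write the term down.

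A reader might infer that the adjustment can never change the primary test. The documents do not support this. The plan allows for 30% of patients missing some post-baseline assessments and relies on a mixed model under missing at random. Such a model uses some between-patient information, so main effects move the result a little.

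The hypothesis in Section 2 is about higher scores at 3 and 6 months, and the follow-up comparisons can be read as visit means. Under that reading the main effect does help, and if a covariate shifted all visits by 0.3 SD per SD it would help almost completely (0.121 to 0.002 SD). This stands for those contrasts, but not for the interaction test that must be significant first.

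The bias is also conditional on an imbalance that is not common. For one covariate and one pair of arms, 0.4 SD corresponds to z = 0.4/√(2/60) = 2.19, two-sided probability about 0.03, or about 0.009 at 86 per arm. Averaged over randomisation, the unadjusted test remains valid. Nothing here shows an inflated type I error.

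**Conclusion.** The point holds for the model as listed. Main-effect adjustment leaves the group-by-time test exactly unchanged with complete data and nearly unchanged under the planned missingness. It does not remove imbalance in a predictor of change or recover precision from discharge location, either in the primary test or in contrasts of change. Contrasts of visit means are partly adjusted.

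The cancellation is algebra and needs no assumption about the trial beyond main-effect entry. The sizes do rest on assumptions: about 0.12 SD of uncorrected difference for the imbalance and slope in step 4, and 2 to 4 points of power for the shares in step 6. The documents give none of these inputs.

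A reader might go on to conclude that the sample size is wrong. It is not: the calculation mentions no covariates and reproduces. Nor does the mention of age group show that the stratification factor was mistaken in the primary model. It appears only in the baseline comparisons and is never called a stratification factor. It is simply not the factor named in Section 4, and the two should be reconciled.

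**What to change.** In Section 8, under the Primary Specific Aim and Secondary Specific Aim 1, state that each mixed model includes discharge location and discharge location-by-time, and that every other adjusting covariate enters with its main effect and its interaction with time. State also that time is categorical.

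With three visits, each two-level or continuous covariate costs 2 degrees of freedom, against 2 × (240 − 4) = 472 within-patient degrees of freedom at 60 per group. The total depends on how many covariates the baseline comparisons select, which is not known in advance. No new data or patients are needed, because discharge location is already used at randomisation and the baseline measures are already collected.

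Moving baseline RBANS to the covariate side, with only post-baseline scores as outcomes, is another route. It changes what group-by-time means and would need the primary test and its power restated, so it is the larger amendment.

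In the baseline comparisons, either replace age group by discharge location or say why age group is used and whether it is also a stratification factor.

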Our team is proposing a 2x2 factorial design randomized controlled trial (RCT) called "Decreasing Alzheimer's Disease and Related Dementias after Delirium-Exercise and Cognitive Training (DDD-ECT)" to evaluate the efficacy of 12 weeks of combined physical exercise and cognitive training on the primary outcome of cognitive function among older ICU survivors who experienced delirium or subsyndromal delirium during their ICU stay. We propose to deliver these interventions via a facilitator-led, small group format using internet-enabled, multiparty-videoconference delivered directly into the participants' homes to achieve the following aims:

**Primary Specific Aim: Determine the effect of the combined physical exercise and cognitive training on the cognitive function of ICU survivors aged 50 and older.** Hypothesis: In comparison to older ICU survivors randomized to attention control or either intervention alone, those randomized to 12 weeks of combined physical exercise and cognitive training will have higher total index cognitive scores as assessed by the Repeatable Battery for the Assessment of Neuropsychological Status (RBANS) at 3 and 6 months post randomization.

**Secondary Specific Aim 1: Determine the effect of the combined physical exercise and cognitive training on physical performance, anxiety and depressive symptoms, and quality of life of ICU survivors aged 65 and older.** Hypotheses: In comparison to older ICU survivors randomized to attention control or either intervention alone, those randomized to 12 weeks of combined physical exercise and cognitive training will have higher physical performance as measured by short physical performance battery (SPPB) and two-minute step test, lower mood and anxiety symptoms as measured by Patient Health Questionnaire (PHQ-9) and Generalized Anxiety Disorder (GAD-7) scale, and higher quality of life as measured by the Medical Outcomes Study 36-item short form (SF-36) at 3 and 6-months post randomization.

**Exploratory Aim 1: To examine the mechanisms of action of combined training.** Hypothesis: At the completion of treatment, the combined intervention group will show reduced serum levels of CRP, IL-1, IL-6, IL-8, TNF- $\alpha$ , S-100 $\beta$ , and GFAP and increased levels of BDNF, VEGF, and IGF-1 compared to the attention control, or either intervention alone groups.

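### Covariates enter the models only when the arms are seen to differ, and the biomarker change ANCOVA does not name the marker's own baseline; the cost is forgone precision and analyst discretion

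*Combined protocol and SAP*

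**What the plan says.** Section 8 (Statistical Considerations) has three covariate rules.

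- **Primary aim (RBANS mixed model):** "adjusting for stratification variables and other potential baseline covariates found to be significantly different in univariate comparisons".
- **Secondary Aim 1:** stratification variables and "other baseline covariates that may be different among the four groups".
- **Exploratory Aim 1 (biomarkers):** changes in each marker "will be calculated and used as the dependent variables in ANCOVA models with group as the independent variable", adjusting for stratification variables and baseline covariates "found to be different among the groups in univariate comparisons". The marker's own baseline value is not mentioned. The follow-up tests are described as being "to compare biomarker levels in the combined training group to the other three groups".

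No significance level is attached to these comparisons. Section 9 (Other data collection) lists roughly 25 baseline variables as possible confounders. That is a pool to draw from and does not fix an adjustment set.

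The Sample Size and Power paragraph claims "81.7% power to detect an overall treatment effect in changes in biomarkers", "using one-way ANOVA and the Power procedure in SAS", that is, without covariates. The hypothesis in Section 2 is worded in levels: "the combined intervention group will show reduced serum levels of CRP", and so on for the other markers.

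**The concern.** After randomisation, baseline differences between arms arise by chance. A rule that admits a covariate because the arms differ on it therefore selects on chance and not on how well the variable predicts outcome. A strong predictor that happens to be balanced is left out and its precision is lost; a weak one that happens to be unbalanced goes in. The model also cannot be written down until baseline data have been seen by arm, and the Secondary Aim 1 wording gives no test at all, so two analysts could reach different models.

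For the biomarkers, the covariate most likely to predict change is the marker's own baseline. If it is subject to the same rule, it will usually be absent. Without it, a comparison of changes and a comparison of 3-month levels are different analyses, and Section 8 uses both words.

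**Working it through.** **Inputs from the documents (Sample Size and Power):** 60 evaluable patients per arm; biomarker effects 0, 0.31, 0.31 and 0.62 SD; alpha 0.05; stated biomarker power 81.7%. For RBANS: effects 0, 0.4, 0.4 and 0.8 SD at 3 and 6 months; correlations 0.2 (3 months apart) and 0.1 (6 months apart); stated power 83%.

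**Assumptions (not in the documents):** a 0.05 entry level; the baseline-to-3-month biomarker correlation rho; the biomarker SDs; and which SD the 0.31 refers to.

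**1. Reproduce the plan's figures.** Biomarkers: the mean effect is 0.31, so the sum of squared deviations is 2 × 0.31² = 0.1922 and lambda = 60 × 0.1922 = 11.53. A noncentral F on 3 and 236 df gives 81.7%, as stated. The primary group-by-time test has lambda 14.84 on 6 numerator df and power 83.3% (Hotelling-Lawley), matching 83%.

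**2. The entry rule.** At 0.05, any one unstratified covariate is left out in about 95% of trials. With 25 independent candidates, 25 × 0.05 = 1.25 enter by chance on average, and at least one enters with probability 1 − 0.95^25 = 72%. The last figure is lower if candidates are correlated (55% at pairwise correlation 0.4).

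**3. Biomarker baseline always included, 0.31 read as SD of change, equal SDs.** Baseline explains R² = (1 − rho)/2 of the variance of change. Power uses lambda/(1 − R²) on 3 and 235 df.

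| rho | R² | lambda | Power, four-arm test | Power, combined vs one single arm (0.31 SD) |
|---|---|---|---|---|
| baseline not included | – | 11.53 | 81.7% | 39% |
| 0.2 | 0.40 | 19.22 | 96.7% | 59% |
| 0.5 | 0.25 | 15.38 | 91.9% | 50% |
| 0.8 | 0.10 | 12.81 | 85.9% | 43% |

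**4. The rule as written, simulated** (4,000 trials per setting, marker baseline admitted only if the arms differ at 0.05). Power is 83.0% at rho 0.2 and 82.2% at rho 0.5, against 96.6% and 91.8% with baseline always in. Baseline enters in about 5% of trials. Type I error across rho 0.2, 0.5 and 0.7 is 3.7% to 4.6%.

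**5. Sensitivity to the assumptions.**

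- *0.31 read as SD of level, equal SDs:* divide 0.31 by √(2(1 − rho)) for change and by √(1 − rho²) for ANCOVA. Power goes from 60%, 82% and 99.7% to 83%, 92% and 99.9% at rho 0.2, 0.5 and 0.8.
- *Unequal SDs, 0.31 read as SD of change:* with k = baseline SD / 3-month SD, R² = (rho − k)²/(k² + 1 − 2·rho·k). At k = 0.67, power is 83% to 90% over the same three correlations; at k = 1.5 it is above 99%. R² is zero when k = rho, and the gain then vanishes.

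**6. Primary test.** A covariate that is constant over time, with one coefficient, shifts all three RBANS values equally and cancels from every within-patient change. With complete data, group-by-time estimates and standard errors with and without such a covariate agree to rounding error. The 3-month standard error is 0.2309 SD = √(2 × 1.6/60), where 1.6 = 2(1 − 0.2) is the variance of a change score. So the primary model, with baseline RBANS as an outcome and free arm means, is also a change comparison. Conditioning on baseline RBANS would raise lambda from 14.84 to 33.25 at the plan's correlations, a ratio of 2.24. The biomarker ratio at rho 0.2 is 19.22/11.53 = 1.67.

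**The case against.** The strongest defence is that nothing stated is wrong. Both power figures were computed without covariates and reproduce, the rule does not inflate type I error, and the biomarker aim is exploratory. All of that stands. A reader might infer a false-positive problem or an overstated power; the documents support neither.

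It can also be said that calling the model an ANCOVA implies adjustment for the marker's baseline. This is weak: Section 8 uses the same term for baseline comparisons adjusted for age group, spells out the biomarker covariates without the marker's baseline, and powers the analysis as a one-way ANOVA.

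The size of the gain depends on a correlation, an SD ratio and a reading of 0.31 SD that the documents do not give. That stands, which is why ranges are shown.

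A reader might infer that the primary aim loses little and that the biomarker analysis carries the main loss. That holds only for extra time-constant covariates. On handling of baseline, the primary model has the same feature, and the ratio in step 6 is larger at the plan's correlations.

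A reader might also see the words change and level as two conflicting planned tests. Section 8 names one dependent variable, the change; the reference to levels in the follow-up comparisons is most naturally loose wording. Finally, Section 8 mentions stratification variables in the plural and an age group, while the Randomization text in Section 4 names discharge location only. That text breaks off in the available copy, so this is a wording point to reconcile and no evidence of a design fault.

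**Conclusion.** The concern holds as a matter of pre-specification and forgone precision. Beyond the stratification variables, covariates enter on observed arm differences, with no level and no fixed set, and the biomarker ANCOVA leaves out the marker's own baseline unless chance imbalance brings it in.

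For the four-arm biomarker test, with 0.31 as SD of change and equal SDs, the power left unused is about 15, 10 or 4 percentage points at correlation 0.2, 0.5 or 0.8. If 0.31 is SD of level, the corresponding gaps are about 24, 10 and 0 points. The gain is near zero if the correlation equals the SD ratio. Under the SD-of-change reading, the contrasts of combined training with a single arm stay weak even after adjustment, at 43% to 59%.

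The complete-data primary group-by-time test is unaffected by extra time-constant covariates. For that aim, the rule costs chiefly a model that is not fixed in advance. Whether the primary analysis should also condition on baseline RBANS is a separate question, and this point makes no ranking between the two analyses.

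**What to change.** 1. **Biomarkers.** In each change ANCOVA, always include that marker's baseline value. It is already measured and costs one degree of freedom per model. Arm contrasts in change and in 3-month level are then identical, so the mixed wording no longer matters.
2. **All models.** Replace difference-based entry with a short set fixed before any baseline data are seen by arm, chosen by the investigators on prognostic grounds from variables already collected. Discharge location, age, years of education and APACHE II score are one example; prior cognition (IQCODE) and the Charlson index are also available. State a rule for missing covariate values, such as the mean pooled across arms. With the example set this costs about three further degrees of freedom and no new data.
3. **Imbalance-based adjustment.** Keep it as a sensitivity analysis only.
4. **Wording.** Reconcile the plural stratification variables and the undefined age group in Section 8 with the Randomization text in Section 4, and state in the sample size paragraph which SD the 0.31 refers to.

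These are changes to the text of the analysis plan only.

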12 weeks of at-home combined physical exercise and cognitive training intervention, consisting of six in-person visits for cognitive training and six telemedicine visits for physical exercise. At 3-month follow-up, the ICU survivors in the active treatment arm tolerated the combined program and had significantly better cognition as measured by the TOWER test, which is a timed objective measure of executive function (median score: 13.0 vs. 7.5, p<0.01) and functional score as measured by the Functional Assessment Questionnaire (median score: 1.0 vs. 8.0, p=0.04). The findings of this study are promising and provide rationale for our proposed trial. However, the study did not control for attention, had a very small sample size with no power to investigate the impact of the intervention on physical performance and it neither measured the ICU survivors overall quality of life nor their depressive and anxiety symptoms. Also, the isolated effects of physical rehabilitation or cognitive therapy on neuropsychiatric outcomes cannot be evaluated, as both interventions were concurrently administered.

Based on the background above, physical exercise and cognitive training hold promise for improving cognitive outcomes of ICU survivors although the current evidence is limited. We plan to further explore these findings through an efficacy, randomized, 2x2 factorial design clinical trial with four treatment arms, a) physical exercise and cognitive training, b) physical exercise, c) cognitive training, and d) attention control. The trial will not only be able to answer the question whether combined physical and cognitive therapies are superior to either of them alone as compared to attention control, but will also shed light on mechanisms of action of the intervention through use of serum biomarkers. An advanced mechanistic understanding of cognitive recovery after delirium will lead to refined interventions to prevent progression to dementia and Alzheimer's disease.

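### The omnibus group-by-time test does not protect the combined-versus-single-training contrasts when training works but combining adds nothing; a false superiority claim can then reach about 8-9% against a 2.5% reference

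*Combined protocol and SAP*

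**What the plan says.** Section 8, Primary Specific Aim, fits a mixed model to RBANS at baseline, 3 and 6 months and tests the group-by-time interaction across four arms. Then: "Post-hoc comparisons will be conducted following a significant interaction between group and time to compare the effect of the combined training group" with attention control, cognitive training only and exercise only, at 3 months (immediate effect) and at 6 months (sustained effect). Three comparators at two visits make six contrasts.

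The text gives no multiplicity adjustment, order of testing, alpha or sidedness for these contrasts. It does not say whether one significant contrast is enough for a claim. An alpha of 0.05 appears only in Sample Size and Power, where the target is the omnibus test: "a sample size of 60 patients in each group will yield 83% power at detecting a significant group by time interaction".

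Section 1 says the trial is to answer "whether combined physical and cognitive therapies are superior to either of them alone as compared to attention control". The primary hypothesis in section 2 is directional: higher RBANS with combined training than with control or with either training alone.

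**The concern.** An omnibus test used as a gate holds the error rate of later contrasts only under the global null, where all four arms are equal. That is not the null that matters for this trial's distinguishing question. The relevant null is that training helps but combining adds nothing. The plan itself assumes that each single training works.

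Under that null the two contrasts with control are real effects and they open the gate. Four contrasts remain that are truly null: combined against each of two single arms, at each of two visits. Nothing written in the plan limits errors among those four. One significant result out of four could be reported as an added benefit of combining when there is none. This concerns type I error and is separate from whether the contrasts have enough power.

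**Working it through.** **Inputs, all from section 8, Sample Size and Power.** "Assuming effect sizes of 0.4 SD in the cognitive training only group and the exercise only groups"; "effect size of 0.8 SD in the combined training group at 3 and 6 month post baseline"; "correlations of 0.2 for outcomes measured 3 month apart and correlations of 0.1 for outcomes measured 6 month apart"; 60 analysable patients per arm; alpha 0.05 for the omnibus test.

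**Step 1: reproduce the plan's power.** In SD units the variance of change from baseline is 2(1 − 0.2) = 1.6 at 3 months and 2(1 − 0.1) = 1.8 at 6 months. The covariance of the two changes is 1 − 0.2 − 0.1 + 0.2 = 0.9. With the same effect at both visits, the weight is (1.6 + 1.8 − 2×0.9)/(1.6×1.8 − 0.9²) = 1.6/2.07 = 0.773. Arm effects 0, 0.4, 0.4, 0.8 have mean 0.4 and sum of squared deviations 0.32. Noncentrality is 60 × 0.32 × 0.773 = 14.84 on 6 df. Power is 82.7% (236 error df) to 83.3% (472 error df), against the stated 83%. Allowing for 30% missing, 60/0.7 rounds up to 86 per arm, and 4 × 86 = 344, as stated.

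**Step 2: the null of interest.** Set control to 0 and all three trainings to δ. The sum of squared deviations is 0.75δ². At δ = 0.8 the noncentrality is 60 × 0.48 × 0.773 = 22.3, so the gate nearly always opens.

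**Step 3: simulate the rule.** Normal data, known variance, complete data, 300,000 trials per setting, 60 per arm. Omnibus test at 0.05, then each contrast at two-sided 0.05 (assumed). Ranges cover contrasts on change from baseline, on follow-up score, and on baseline-adjusted score. The count is any rejection among the four combined-versus-single contrasts.

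| All trainings equal at δ | Gate opens | False difference, either direction | False superiority of combined |
|---|---|---|---|
| 0 (all four arms equal) | 4.6% | 2.3-3.1% | 1.2-1.6% |
| 0.4 SD | 36% | 8.9-10.4% | 4.5-5.1% |
| 0.6 SD | 75% | 14.5-14.7% | 7.3-7.5% |
| 0.8 SD | 96% | 15.9-16.8% | 7.9-8.6% |
| 1.0 SD or more | about 100% | 15.9-17.2% | 8.0-8.7% |

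With 86 per arm, δ = 0.8 gives 16.0-17.1% and 8.1-8.5%. At δ = 0.4 with 86 per arm, false superiority is 5.9-6.3%.

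**Step 4: plausibility.** Four independent tests would give 1 − 0.95⁴ = 18.5% in either direction and 1 − 0.975⁴ = 9.6% in favour of combined. The simulated maxima lie a little below, as expected when the contrasts share the combined arm.

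**Step 5: only one single arm equals combined.** With exercise inert and cognitive = combined = 0.8 SD, two contrasts are null. A false difference occurs in about 9.5-9.7% of trials (follow-up scores) and false superiority in 4.4-4.9%.

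**The case against.** A reader might infer that the plan falsely declares combined training superior in 17% of trials. The documents do not support that. The 17% counts differences in either direction, and about half of them have combined looking worse. The hypothesis is directional, and in that direction the maximum is about 8-9%. The errors also come from four contrasts; the two against control are true effects in this scenario.

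The maximum needs every training to deliver about 0.8 SD or more, twice what the plan assumes for a single training. At 0.4 SD and 60 per arm, false superiority is about 5%. That stands as a limit on size, although it is still twice 2.5%.

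Nor do the documents say that contrasts are tested unadjusted at 0.05 or that one of four suffices. The hypothesis can be read as requiring combined to beat both single arms. On that reading, with all trainings equal, falsely beating both at the same visit happens in only about 0.5-0.9% of trials. This is the strongest counter-argument, but it is incomplete. The plan does not state that rule. If only one single arm matches combined and the other is inert, the contrast with the inert arm is almost always won (0.8/√(2/60) = 4.4 standard errors at a visit), so the both-arms rule adds little and the two-visit rate stays near the 4.4-4.9% of Step 5.

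**Conclusion.** The concern holds in limited form. The one error control written into the primary analysis works when all arms are equal and fails when training works but combining adds nothing. The size is up to about 16-17% for any false combined-versus-single difference and up to about 8-9% for a false superiority claim, some 3.4 times the 2.5% reference (8.6/2.5). With all effects at 0.4 SD and 60 per arm the figures are about 9-10% and 5%.

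These figures rest on unadjusted two-sided 0.05 contrasts, any one of which is enough for a claim, and on the plan's correlations with normal, complete data. The first two conditions are assumptions that fill a silence; they are not rules the plan lays down.

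**What to change.** In section 8, Primary Specific Aim, replace the open post-hoc step with two statements:

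1. The six contrasts of combined training with the other three arms, at 3 and at 6 months, are tested with Holm's procedure at family-wise two-sided 0.05 (smallest p-value against 0.05/6 = 0.0083, then 0.05/5, and so on).
2. Superiority over single training at a visit is claimed only if combined beats both single arms at that visit.

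Family-wise error is then at most 5% whichever arms are equal. The change is to wording only and needs no extra patients.

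The cost, under the plan's effects with 60 per arm, the omnibus test kept and scores compared at each visit: power for combined versus control goes from about 83% to 82% at each visit, and power to beat both single arms at a visit from about 38% to 29%. For change-from-baseline contrasts power is lower and the loss against control is larger, because the 3-month standard error rises from √(2/60) = 0.183 to √(2×1.6/60) = 0.231 SD. The plan should therefore also say which contrast it means.

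A fixed order that puts all 6-month tests behind beating both single arms at 3 months would also control the error, but at a high price for the sustained effect. At 60 per arm, 6-month power falls from 83% to 38% against control and from 38% to 19% for beating both single arms. At 86 per arm the falls are 95% to 59% and 59% to 39%. It should not be used unless that loss is disclosed and accepted.
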